10.2.2 Renal safety monitoring

To ensure participant safety and enhance reliability in determining the nephrotoxicity potential of an investigational drug, a standardized process for identification, monitoring and evaluation of renal events has to be followed.

Every renal laboratory trigger or renal event as defined in [Table 16-6](#) ([Section 16.4](#) (Appendix 4)) should be followed up by the investigator or designated personnel at the trial site as summarized in [Table 16-7](#) ([Section 16.4](#) (Appendix 4)).

10.2.3 Other safety monitoring

The frequency and severity of the AEs listed below will be monitored during the study. They will be reviewed by the DMC at regular intervals.

- ISRs (see also [Section 8.4.4.3](#)), hypersensitivity reactions and immune-mediated reactions
- Hepatobiliary AEs and liver-related biochemical abnormalities (see also [Section 6.5.2.1](#) and [Section 10.2.1](#))
- Musculoskeletal AEs and muscle-related biochemical abnormalities (e.g. C(P)K)
- Neurological or psychiatric AEs
- New onset of diabetes or worsening of glycemic control in diabetics (see also [Section 8.4.4.5](#))

10.2.4 Data Monitoring Committee

This study will include a DMC, which will function independently of all other individuals associated with the conduct of this clinical trial, including the site investigators participating in the study. The DMC will assess at defined intervals the progress of the clinical trial, review safety data, and recommend to the sponsor whether to continue, modify or terminate the trial.

It is anticipated that the DMC will review safety data 90 days after all participants received the first injection of study drug and every 3 months thereafter until EOS, unless requested otherwise by the DMC.

Specific details regarding composition, responsibilities, data monitoring and meeting frequency, and documentation of DMC reports, minutes, and recommendations will be described in a separate DMC charter that is established between the sponsor and the DMC.

10.2.5 Steering Committee

The Steering Committee (SC) will be established comprising representatives associated with the trial, but not being members of the DMC. Novartis representatives from the Global Clinical Team can be present at the SC meetings.

The SC will ensure transparent management of the study according to the protocol through recommending and approving modifications as circumstances require. The SC will review protocol amendments as appropriate. Together with the clinical team, the SC will also develop recommendations for publications of study results including authorship rules. The details of the role of the SC will be defined in the SC charter.

11 Data Collection and Database management

11.1 Data collection

Designated investigator staff will enter the data required by the protocol into eCRFs. The eCRFs have been built using fully validated secure web-enabled software that conforms to 21 Code of Federal Regulation (CFR) Part 11 requirements, Investigator site staff will not be given access to the Electronic Data Capture (EDC) system until they have been trained. Automatic validation programs check for data discrepancies in the eCRFs, allow modification and/or verification of the entered data by the investigator staff.

The investigator/designee is responsible for assuring that the data entered into the eCRF is complete, accurate, and that entry and updates are performed in a timely manner. The Investigator must certify that the data entered are complete and accurate

After final database lock, the investigator will receive copies of the participant data for archiving at the investigational site.

All data should be recorded, handled and stored in a way that allows its accurate reporting, interpretation, and verification.

11.2 Database management and quality control

Novartis personnel (or designated Contract Research Organization (CRO)) will review the data entered by investigational staff for completeness and accuracy. Electronic data queries stating the nature of the problem and requesting clarification will be created for discrepancies and missing values and sent to the investigational site via the EDC system. Designated investigator site staff are required to respond promptly to queries and to make any necessary changes to the data.

Concomitant treatments and prior medications entered into the database will be coded using the World Health Organization (WHO) Drug Reference List, which employs the Anatomical Therapeutic Chemical classification system. Medical history/current medical conditions and AEs will be coded using the Medical Dictionary for Regulatory Activities (MedDRA) terminology.

Dates of screenings, randomizations, screen failures and study completion, as well as randomization codes and data about all study treatment (s) dispensed and all dosage changes will be tracked using an IRT. The system will be supplied by a vendor, who will also manage the database. The data will be sent electronically to Novartis (or a designated CRO) at specific timelines.

Each occurrence of a code break via IRT will be reported to the clinical team and monitor. The code break functionality will remain available until study shut down or upon request of Novartis.

Once all the necessary actions have been completed and the database has been declared to be complete and accurate, it will be locked and the treatment codes will be unblinded and made available for data analysis. Any changes to the database after that time can only be made after written agreement by Novartis Development management.

11.3 Site monitoring

Before study initiation, at a site initiation visit or at an investigator's meeting, a Novartis representative will review the protocol and data capture requirements (i.e. eCRFs) with the investigators and their staff. During the study, Novartis employs several methods of ensuring protocol and GCP compliance and the quality/integrity of the sites' data. The field monitor will visit the site to check the completeness of participant records, the accuracy of data capture / data entry, the adherence to the protocol and to GCP, the progress of enrollment, and to ensure that study treatment is being stored, dispensed, and accounted for according to specifications. Key study personnel must be available to assist the field monitor during these visits.

The investigator must maintain source documents for each participant in the study, consisting of case and visit notes (hospital or clinic medical records) containing demographic and medical information, laboratory data, ECGs, and the results of any other tests or assessments. All information on eCRFs must be traceable to these source documents in the participant's file. The investigator must also keep the original signed ICF and the original signed assent form, if applicable (a signed copy is given to the participant's parent(s)/legal representative(s)/participant (if applicable)).

The investigator must give the monitor access to all relevant source documents to confirm their consistency with the data capture and/or data entry. Novartis monitoring standards require full verification for the presence of informed consent, adherence to the inclusion/exclusion criteria, documentation of SAEs, and of data that will be used for all primary variables. Additional checks of the consistency of the source data with the eCRFs are performed according to the study-specific monitoring plan. No information in source documents about the identity of the participants will be disclosed.

12 Data analysis and statistical methods

Details of the statistical analysis and data reporting will be summarized in the Statistical Analysis Plan (SAP) document finalized before data lock. Any data analysis carried out independently by the investigator should be submitted to Novartis before publication or presentation.

Efficacy and safety analyses of Part 1 data will be performed after all participants have completed the Day 360 visit or discontinued prior to the Day 360 visit. All available data from the clinical database will be included in the analysis. This analysis will be unblinded and reviewed by the CTT.

12.1 Analysis sets

The Full Analysis Set (FAS) comprises of all randomized participants with the exception of those mis-randomized participants who did not receive study drug. Mis-randomized participants are defined as not qualified for randomization and are inadvertently randomized into the study. According to the intent to treat principle, participants will be analyzed according to the treatment they have been assigned to during the randomization procedure. The FAS will be used in analyses for the primary, secondary, [REDACTED] objectives.

The Safety Set includes all participants who received at least one dose of study treatment. Participants will be analyzed according to the study treatment received. This will be the primary population for the safety analyses.

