Women of child bearing potential and her parent(s)/legal representative(s) must be informed that taking the study treatment may involve unknown risks to the fetus if pregnancy were to occur during the study and agree that in order to participate in the study they must adhere to the contraception requirements.

8 Visit schedule and assessments

The Assessment Schedule ([Table 8-1](#)) lists all of the assessments when they are performed. All data obtained from these assessments must be supported in the participant's source documentation.

Participants should be seen for all visits/assessments as outlined in the Assessment Schedule or as close to the designated day/time as possible. Missed or rescheduled visits should not lead to automatic discontinuation.

Participants who prematurely and permanently discontinue from study treatment will continue to be followed up in the study according to the Assessment Schedule unless informed consent is withdrawn.

Participants who prematurely discontinue the study for any reason [e.g. if a participant's parent(s)/legal representative(s) / a participant (if applicable) decide to prematurely and permanently discontinue the participant from study treatment and decline further follow-up visits] should be scheduled for an EOS visit as soon as possible. At this final visit, AEs and concomitant medications should be recorded in the corresponding eCRFs.

Participants will have to comply with the following restrictions:

- Participants should have fasted for at least 8 hours for all visits for fasting lipids/lipoproteins/PCSK9 and glucose blood samples (if the participant has not fasted, the collection of laboratory evaluations must be rescheduled)
- Participants must refrain from unaccustomed strenuous physical exercise for 48 hours before the screening and any study visit until the follow-up has been completed
- Blood donation will not be allowed at any time during the study

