12.2 Participant demographics and other baseline characteristics

Demographic and other baseline data including medical history will be summarized descriptively by treatment group for the FAS.

Categorical data will be presented as frequencies and percentages by treatment group. For continuous data, non-missing observations, mean, standard deviation, median, minimum, and maximum will be presented. For continuous data, the 1st and 3rd quartile will also be presented by treatment group.

Relevant medical histories and current medical conditions at baseline will be summarized separately by system organ class and preferred term, by treatment group. Histories of statin intolerance and underlying genetic mutation will be summarized by treatment group.

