12.5 Analysis of secondary endpoints/estimands

12.5.1 Efficacy and/or Pharmacodynamic endpoint(s)

Secondary efficacy endpoints include:

- Time-adjusted percent change in LDL-C from baseline after Day 90 and up to Day 330 (Year 1)
- Percent change and absolute change in LDL-C from baseline to each assessment time up to Day 720 (Year 2)
- Percent change and absolute change in Apo B from baseline to each assessment time up to Day 720 (Year 2)
- Percent change and absolute change in Lp(a) from baseline to each assessment time up to Day 720 (Year 2)
- Percent change and absolute change in non-HDL-C from baseline to each assessment time up to Day 720 (Year 2)
- Percent change and absolute change in total cholesterol from baseline to each assessment time up to Day 720 (Year 2)
- Percent change and absolute change in triglycerides from baseline to each assessment time up to Day 720 (Year 2)
- Percent change and absolute change in HDL-C from baseline to each assessment time up to Day 720 (Year 2)
- Percent change and absolute change in VLDL-C from baseline to each assessment time up to Day 720 (Year 2)
- Percent change and absolute change in Apo A1 from baseline to each assessment time up to Day 720 (Year 2)
- Percent change and absolute change in PCSK9 from baseline to each assessment time up to Day 720 (Year 2)

Descriptive summaries by treatment group will be presented.

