2.2 Analysis sets

The Screened Set (SCR) includes all participants who provided study informed consent.

The Randomized Set (RAN) consists of all participants who received a randomization number, regardless of whether double blind treatment received or not.

The Full Analysis Set (FAS) consists of all randomized participants with the exception of those mis-randomized participants who did not receive study drug. Mis-randomized participants are defined as not qualified for randomization and were inadvertently randomized into the study. According to the intent to treat principle, participants will be analyzed according to the treatment they have been assigned to during the randomization procedure. The FAS will be used in analyses for the primary, secondary, [REDACTED] efficacy objectives in Part 1.

The Safety Set (SAF) includes all participants who received at least one dose of study treatment. Participants will be analyzed according to the study treatment received. This will be the primary population for the safety analyses in Part 1.

Note that the Safety Set allows the inclusion of non-randomized participants who receive double-blind treatment in error.

The Open-label Phase Analysis Set (OAS) includes all participants who entered in study Part 2 and received at least one dose of study treatment in Part 2. The OAS will be used to analyze the data from participants who entered Part 2.

Note that in Part 1 the number of participants in FAS equals the number of participants in SAF, so only one open-label phase analysis set is defined for Part 2.

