2.3.2 Demographics and other baseline characteristics

Demographic and other baseline data including age, race, gender, ethnicity, country, region (North America, Europe, Other), baseline characteristics such as body height, weight, BMI, waist circumference, smoking status, number of pack years, alcohol history, baseline disease characteristics including HoFH underlying genetic mutation(s), LDL-C, TC (total cholesterol), TG (triglycerides), PCSK9, baseline use of statins or other lipid-modifying therapies (yes, no), status of statin intolerance, baseline diabetes status as determined by fasting plasma glucose and HbA_{1C}, baseline kidney function based on eGFR, baseline SBP, DBP, pulse will be summarized descriptively by treatment group. Listings will also be provided.

Categorical data will be presented as frequencies and percentages by treatment group. For continuous data, non-missing observations, mean, standard deviation, median, 1st and 3rd quartile, minimum, and maximum will be presented. For Part 1 analysis, these data will be summarized using RAN.

No inferential statistics will be provided for baseline comparability among the treatment groups.

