2.11 Interim analysis

Interim analyses are planned for the monitoring of participants' safety and will be performed as determined by the DMC (see DMC charter). Interim safety analyses before the unblinding for the analysis of Part 1 of the study will be performed by an independent statistician/programmer who will not be involved in the trial conduct. The interim results will be reviewed by the independent DMC.

3 Sample size calculation

The sample size for this study was selected based on feasibility.

4 Change to protocol specified analyses

No change from protocol specified analysis was made.

5 Appendix

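### Without declaring a change, the SAP moves baseline tables from the FAS to all randomised participants and Day 450–720 lipids to a set requiring a Part 2 dose

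*Protocol*

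**What the plan says.** **Protocol.** Section 12.1 defines the FAS as everyone randomised, grouped as randomised, apart from mis-randomised participants who never received study drug. It then states: "The FAS will be used in analyses for the primary, secondary, [REDACTED] objectives". Section 12.5.1 lists secondary endpoints for LDL-C, the other lipids and PCSK9 at each assessment up to Day 720. Section 12.2 adds: "Demographic and other baseline data including medical history will be summarized descriptively by treatment group for the FAS". Section 8 keeps people in the study after they stop drug, unless consent is withdrawn: "Participants who prematurely and permanently discontinue from study treatment will continue to be followed up in the study according to the Assessment Schedule".

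**SAP.** Section 2.2 defines RAN (everyone given a randomisation number), the FAS, the safety set, and the OAS (entered Part 2 and dosed at least once there). It restricts the FAS to Part 1 efficacy and assigns the OAS to Part 2. After noting that the FAS and the safety set have equal numbers in Part 1, it concludes: "so only one open-label phase analysis set is defined for Part 2". For demographics and baseline characteristics, including baseline LDL-C, Section 2.3.2 says: "For Part 1 analysis, these data will be summarized using RAN". Section 2.3.3 does the same for medical history. Section 2.1 starts Part 2 data after the Day 360 injection. Section 4 says: "No change from protocol specified analysis was made".

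**The concern.** Two analysis sets differ between the documents, and the section meant to record such differences says there are none.

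The long-term lipid set matters more. Membership of the OAS depends on what happens after randomisation. A participant who stops early but keeps attending is in the FAS and counts at Day 360, then disappears from Day 450 onwards. With about a dozen participants, one departure can move a group mean visibly, and the movement could be read as a change in drug effect. SAP Section 2.6.4 also plans treatment differences for several parameters at both Day 330 and Day 720. Under Section 2.2 the first rests on the FAS and the second on the OAS.

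The baseline change is smaller. RAN adds back exactly the undosed, mis-randomised participants whom the FAS removes. SAP Section 2.5.6 says the covariate-adjusted model will not be run, so the baseline table becomes a main guide to chance imbalance. It should describe the people in the primary analysis.

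**Working it through.** **1. The sets side by side**

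| Data | Protocol | SAP |
|---|---|---|
| Demographics, baseline, medical history | FAS (12.2) | RAN (2.3.2, 2.3.3) |
| Primary, Day 330 | FAS (12.1) | FAS (2.2) |
| Lipids and PCSK9 to Day 360, pre-dose | FAS (12.1, 12.5.1) | FAS (2.1, 2.2) |
| Lipids and PCSK9 after Day 360 | FAS (12.1, 12.5.1) | OAS (2.1, 2.2) |
| Combined Part 1 and 2 efficacy display | not described | no set named (Appendix 5.3) |

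The post-Day-360 samples are LDL-C at Days 450, 510, 630 and 720, and the other lipids and PCSK9 at Days 510 and 720 (Protocol 8.3.1, 8.3.2). SAP Section 2.6 names no set itself, so the OAS follows from Sections 2.1 and 2.2 read together.

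**2. Who is affected.** In normal conduct the OAS lies within the FAS and the FAS within RAN.
- FAS but not OAS: no Part 2 dose. The loss is real only for those who stop before Day 360, do not restart and still give samples.
- RAN but not FAS: mis-randomised and never dosed. The documents give no count, and it may be zero. The SAP's note on equal FAS and safety-set numbers does not settle this, because it does not compare either set with RAN.

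**3. Size for the long-term means.** There is no planned figure to reproduce, because the sample size rests on feasibility. About 12 participants at 2:1 gives 12 × 2/3 = 8 and 12 × 1/3 = 4. These are planned sizes; actual arm sizes are not stated. Let the group have n participants, let one lack a Part 2 dose and have percentage change x, and let the others average m:

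- FAS mean = [(n − 1)m + x]/n
- OAS mean = m
- size of the gap = |m − x|/n

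Assume m = −30% and x = 0 (back at baseline):

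- n = 8: (7 × −30 + 0)/8 = −26.25%, against −30%, a gap of 3.75 points.
- n = 4: (3 × −30 + 0)/4 = −22.5%, against −30%, a gap of 7.5 points.

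For m from −20% to −40% the gap is 20/8 = 2.5 to 40/8 = 5 points (n = 8), or 20/4 = 5 to 40/4 = 10 points (n = 4). For any difference of 10 to 50 points between that person and the rest, it is 1.25 to 6.25 points (n = 8) or 2.5 to 12.5 points (n = 4). If everyone is dosed in Part 2, it is zero. The OAS looks better when the omitted person responds less than the others, and worse when that person responds more.

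**4. Size for the baseline table.** One extra undosed participant would be one of five in the placebo column. With assumed values of 120 mg/dL for that person and a mean of 300 mg/dL for the other four: (4 × 300 + 120)/5 = 264 mg/dL, which is 12% lower. Both values are illustrative. With no such participant, the RAN and FAS tables are identical.

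**The case against.** **What stands**
- Part 2 has no comparator, Protocol Section 2.2 defines no secondary estimand, and Section 12 leaves detail to the SAP. A set of participants who entered Part 2 is a legitimate choice for an uncontrolled extension.
- A placebo participant without a Part 2 dose never received inclisiran. Including that person in a placebo-to-inclisiran mean answers a different question, so the two sets should be shown together rather than one replacing the other.
- Full return to baseline is an extreme case soon after stopping. Protocol Section 4.2 describes an effect lasting more than six months after a single dose.
- Randomisation follows confirmed eligibility at the Day 1 visit (Protocol 6.3.2), so a difference between RAN and the FAS needs an error plus no dose.
- Set counts, disposition by part, LDL-C summaries by subject and listings are planned (SAP 2.3.1, 2.6.2), so a careful reader could see who leaves.

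**What does not answer the point.** Freedom to choose a set does not make a statement of no change correct. Listings let a reader rebuild the FAS result but do not report it.

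**Stronger readings the documents do not support**
- That one LDL-C time course rests on three populations. It rests on two, the FAS and then the OAS. RAN is named only for disposition, baseline and medical-history tables, and change is measured from each participant's own pre-dose value (SAP 2.1.1).
- That the OAS contains only those who kept taking drug. One Part 2 dose is enough, and for the inclisiran arm the Day 360 injection is blinded placebo.
- That the SAP justifies the dosing requirement by the equality of the FAS and the safety set. That note only explains why there is one open-label set rather than separate efficacy and safety versions.
- That everyone who stops will supply later LDL-C values. Protocol Section 9.1.1 sets a minimum of treatments and adverse events, asks for full clinic assessments where possible, and allows treatment to be restarted.

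**Conclusion.** The conflict is in the text. The protocol puts baseline data and secondary efficacy to Day 720 on the FAS. The SAP uses RAN for the baseline and medical-history tables and the OAS for lipids and PCSK9 after Day 360, and Section 4 wrongly reports no change.

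The practical effect is confined to secondary and descriptive output. On planned arm sizes, one followed participant without a Part 2 dose would shift a Day 450–720 mean by 3.75 points (n = 8) or 7.5 points (n = 4), assuming −30% in the others and a return to baseline in that person. There is no numerical effect if everyone is dosed in Part 2 and nobody was both mis-randomised and undosed. The primary Day 330 analysis uses the FAS in both documents, and no hypothesis is tested. This is worth correcting because the correction is cheap, not because it threatens the main result.

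**What to change.** 1. SAP 2.3.2 and 2.3.3: present the baseline and medical-history tables on the FAS, as the protocol says.
2. SAP 2.2 and 2.6: report Day 450–720 lipids and PCSK9 on the FAS as randomised, with n at each visit. Show the OAS version beside it, labelled as participants with at least one Part 2 dose and not as on-treatment.
3. SAP Appendix 5.3: name the analysis set for the combined Part 1 and 2 efficacy display.
4. SAP Section 4: replace the statement of no change with a list of any set that still departs from the protocol, with the reason.

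The note on equal FAS and safety-set numbers can stay. The cost is population flags, SAP wording and a few extra table rows, with no new data. The long-term figure may come out slightly less favourable.
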